#### 5.4.6 Crude incidence and $100*(1-\alpha)\%$ confidence interval

For  $n$  subjects, each at risk to experience a certain event with probability  $\pi$ , the crude incidence is estimated as  $p=x/n$ , where  $x$  is the number of subjects with the event.

Absolute and relative frequencies will be displayed as well as 95% confidence interval for the relative frequency based on the score method including continuity correction (Newcombe 1998).

With  $z$  as  $(1 - \alpha / 2)$ -quantile of the standard normal distribution (SAS:  $z=PROBIT(1-\alpha/2)$ ),  $n$  as total number of subjects (i.e. number of subjects in the denominator), and  $p$  as estimated crude incidence (number of subjects with event /  $n$ ) it is  $q = 1-p$ .

Then the lower limit is:

$$L = 100 \times \max \left( 0, \frac{2np + z^2 - 1 - z \sqrt{z^2 - 2 - \frac{1}{n} + 4p(nq + 1)}}{2(n + z^2)} \right)$$

and the upper limit is:

$$U = 100 \times \min \left( 1, \frac{2np + z^2 + 1 + z \sqrt{z^2 + 2 - \frac{1}{n} + 4p(nq - 1)}}{2(n + z^2)} \right)$$

In addition, if  $L > p \times 100$  then  $L = p \times 100$  and if  $U < p \times 100$  then  $U = p \times 100$ .

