3.2 Rationale for study design

The subject population will be described in more detail in Section 4 below.

The two visit Screening Period is designed to allow for both (1) washout of prohibited medications, and [REDACTED]

The randomized, blinded, parallel-group design used in this study is based on the primary focus of this study, which is to estimate the difference in clinical response between either remaining on 150 mg or escalating to 300 mg of secukinumab after not achieving a measured state of inactive disease at the Week 12 and Week 16 time points. The responder status at Week 12 and Week 16, as well as the primary objective at Week 52 is determined with the validated ASDAS clinical scoring measure of disease activity status which will establish patients who score within the “inactive disease” classification of this measure (a total score of < 1.3). Week 52 has been selected as the primary analysis time point to allow sufficient time (36 weeks) for a clinical response to be observed following dose escalation to 300 mg at Week 16 vs those patients who remain on 150 mg for the entire 52-week period.

Following the Week 16 visit, randomized inadequate responder patients and investigators will be blind to the dose of secukinumab through the use of a matched placebo injection (identical in appearance) in the 150 mg s.c. group. The blinding of the secukinumab treatments (150 mg or 300 mg) will allow for an evaluation of a potential dose-response of the 150 mg and 300 mg secukinumab doses on both efficacy and safety outcomes.

Responder patients, those who achieve ASDAS inactive disease at Week 12 and Week 16, will continue on secukinumab 150 mg to evaluate the longer-term treatment response up to Week 52. To support the integrity of the blind for the randomized inadequate responder group, the responder patients will also be dose blinded between Week 16 and Week 48 by receiving a single matching placebo injection to their secukinumab 150 mg injection. Thus, all responder and inadequate responder patients will be blinded to dose and will receive two matched injections every 4 weeks. While the responder group is not the primary focus of this study, this subgroup will provide meaningful exploratory analyses of the clinical characteristics and duration of response in patients who achieve a high-level efficacious response to secukinumab at Week 16.

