### **2.5.4 Supportive analyses**

A 95% confidence interval for the difference between the two treatment groups in the proportion of patients who have ASDAS inactive disease response will be calculated using the normal approximation to the binomial distribution for the Full Analysis Set.

The analysis will be performed at each time point in Treatment Period 2.

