### 2.8.1 Adverse events (AEs)

The crude incidence of treatment emergent adverse events (TEAEs) will be summarized by primary system organ class (SOC) and preferred term (PT) for Treatment Period 1 and Treatment Period 2.

Treatment-emergent adverse events (TEAEs) are defined as follows:

- For Treatment Period 1, TEAEs are those AEs that started on or after the first dose date of study treatment, or events present prior to the first dose date of study treatment but increased in severity based on preferred term and the earlier of the last dose date in Treatment Period 1 + 84 days or prior to the first dose date in Treatment Period 2.
- For Treatment Period 2, TEAEs are those AEs that started on or after the first dose date of study treatment in Treatment Period 2 and on or before the last dose date + 84 days.

In addition, exposure time-adjusted rates (incidence rate) including 95% confidence intervals will be provided for entire treatment period to adjust for differences in exposure. For the entire treatment period, TEAEs are those AEs that started on or after the first dose of study treatment, or events present prior to the first dose of study treatment but increased in severity based on preferred term and on or before last dose date + 84 days. For summaries over the entire treatment period, patients who switched from secukinumab 150 mg to secukinumab 300 mg will appear in both treatment groups.

Crude incidence rates and exposure-adjusted incidence rates will be graphically presented for all TEAEs and serious TEAEs along with 95% confidence intervals, by system organ class.

Adverse events will be summarized by presenting, for each treatment group, the number and percentage of patients having at least one AE, having an AE in each primary system organ class and having each individual AE (preferred term). Summaries (crude incidences only) will also be presented for AEs by severity and for study treatment related AEs. If a particular AE 'severity' is missing, this variable will be listed as missing and treated as missing in summaries. If a subject reported more than one adverse event with the same preferred term, the adverse event with the greatest severity will be presented. If a subject reported more than one adverse

event within the same primary system organ class, the subject will be counted only once with the greatest severity at the system organ class level, where applicable.

Separate summaries will be provided for

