## 3 Sample size calculation

The sample size was calculated based on the primary efficacy variable (i.e., ASDAS inactive disease response) at Week 52 for the Full Analysis Set. The expected ASDAS inactive disease response rates for secukinumab 300 mg and 150 mg treatment groups at Week 52 are 20% and 10%, respectively (corresponding to an odds ratio of 2.25), partly based on results from AIN457F2310 (MEASURE 2) study. With approximately 97 patients in each treatment group (total of 194 randomized patients), one will be able to estimate the difference between ASDAS inactive disease response rates of the two treatment groups at Week 52 with a “margin of error” (half-width of confidence interval) of 10% (corresponding to a standard error of 5%) for a two-sided 95% confidence interval (Julious and Patterson, 2004; nQuery Advisor 7.0).

It is expected that the study will need to enroll approximately 270 patients for the 16-week open-label period, to randomize approximately 194 patients who do not achieve ASDAS inactive disease status at Week 16 (inadequate responders). This assumes that 10% of the 270 enrolled patients will discontinue during the 16-week open-label period; among the remaining enrolled patients, it is assumed that approximately 10% will be responders, 80% will be inadequate responders, and 10% will be non-responders.

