#### **5.4.5 Exposure-adjusted incidence rate and $100*(1-\alpha)\%$ confidence interval**

It will be assumed that for each of  $n$  subjects in a clinical trial the time  $t_j$  ( $j=1, \dots, n$ ) to the first occurrence of a certain event is observed, or if the event was not experienced, the (censored) time to the end of the observation period. The total exposure time will be the total number of days with an actual dose greater than zero summed up over all patients, and then divided by 365.25 days. Incidence rate will be calculated per 100 patient years.

The sequence of first occurrences of an event will be modeled to follow approximately a Poisson process with constant intensity  $\theta$ . The rate parameter  $\theta$  will be estimated as  $\lambda = D/T$ , where  $T = \sum t_j$ , ( $j=1, \dots, n$ ) and  $D$  is the number of subjects with at least one event. Conditionally on  $T$ , an exact  $100*(1 - \alpha)\%$  confidence interval for a Poisson variable with parameter  $\theta T$  and observed value  $D$  can be obtained based on (Garwood,1936), from which an exact  $100*(1 - \alpha)\%$  confidence interval for  $D/T$  will be derived as follows (Sahai and Anwer, 1993; Ulm, 1990):

Lower confidence limit:

$$L = \frac{0.5c_{\alpha/2, 2D}}{T} \text{ for } D > 0, 0 \text{ otherwise,}$$

Upper confidence limit :

$$U = \frac{0.5c_{1-\alpha/2, 2D+2}}{T}$$

where  $c_{\alpha, k}$  is the  $\alpha$  th quantile of the Chi-square distribution with  $k$  degrees of freedom.

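### In the readable text, adverse events get per-group intervals only; a descriptive 300 mg minus 150 mg risk difference with its own interval would be a cheap improvement

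*SAP*

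**What the plan says.** Protocol 3.2 explains that blinding the two doses "will allow for an evaluation of a potential dose-response of the 150 mg and 300 mg secukinumab doses on both efficacy and safety outcomes".

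The readable SAP plans two kinds of interval for adverse events:

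- **Crude incidence (SAP 5.4.6).** A "95% confidence interval for the relative frequency based on the score method including continuity correction", for one proportion at a time.
- **Exposure-adjusted rate (SAP 2.8.1 and 5.4.5).** Here "exposure time-adjusted rates (incidence rate) including 95% confidence intervals will be provided for entire treatment period to adjust for differences in exposure". The model is that "The sequence of first occurrences of an event will be modeled to follow approximately a Poisson process with constant intensity", with exact limits for one group at a time.

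On display, SAP 2.8.1 says "Crude incidence rates and exposure-adjusted incidence rates will be graphically presented for all TEAEs and serious TEAEs along with 95% confidence intervals". These plots are split per organ class. The same section also tabulates the number and percentage of patients with events in each treatment group. SAP 2.8 presents Treatment Period 2 results separately for responders and for each randomised arm.

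Efficacy proportions are handled differently. SAP 2.5.4 plans "A 95% confidence interval for the difference between the two treatment groups in the proportion of patients who have ASDAS inactive disease response", and SAP 2.7.2 does the same for the binary secondary variables. Neither SAP 2.8, 5.4.5 and 5.4.6 nor Protocol 9.5.2 defines a risk difference, a ratio or any other between-dose interval for adverse events. SAP 2.8 mentions summarising risk derived from adverse events but attaches no method to it.

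**The concern.** The randomised arms in Treatment Period 2 give the one comparison of 300 mg with 150 mg on safety that randomisation protects. The plan estimates the contrast between these arms, with its uncertainty, for efficacy proportions but not for adverse events.

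The exposure-adjusted rates do not fill the gap. They cover the entire treatment period, where "patients who switched from secukinumab 150 mg to secukinumab 300 mg will appear in both treatment groups". SAP 2.4.1 defines the entire-period groups simply as 150 mg and 300 mg, so the 150 mg group also takes in open-label exposure and the non-randomised responders. The two groups share patients and are not the randomised comparison.

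What remains for judging uncertainty is a pair of separate intervals. Checking whether two 95% intervals overlap is much stricter than checking whether a 95% interval for the difference excludes zero, so a moderate dose-related increase can look unremarkable on the planned plot.

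**Working it through.** **Inputs.** 97 patients per arm, 1:1 allocation and two-sided 95% intervals (SAP section 3 and 1.1). The per-arm limits are coded as printed in SAP 5.4.6. The documents give no adverse-event rates, so every rate below is an assumption and a range is shown. The Safety Set arms are assumed to be close to the randomised size.

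**The plan's own figure.** For efficacy rates of 20% and 10% and a half-width of 0.10:

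n = 1.96² × (0.20×0.80 + 0.10×0.90) / 0.10² = 3.8416 × 0.25 / 0.01 = 96.04, rounded up to 97.

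At 97 per arm the half-width is 9.95 points. The plan's sample size reproduces.

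**One worked example: 22/97 on 300 mg, 10/97 on 150 mg.**

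- Planned per-arm intervals: 22.7% (15.0 to 32.5) and 10.3% (5.3 to 18.6). They overlap.
- Difference: 22.68 − 10.31 = 12.4 points.
- Score limits without correction, needed for the Newcombe interval: 15.48 to 31.96 and 5.70 to 17.95.
- Lower limit: 12.37 − √[(22.68 − 15.48)² + (17.95 − 10.31)²] = 12.37 − √(51.8 + 58.4) = 12.37 − 10.50 = 1.9.
- Upper limit: 12.37 + √[(31.96 − 22.68)² + (10.31 − 5.70)²] = 12.37 + √(86.1 + 21.3) = 12.37 + 10.36 = 22.7.

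The same data give overlapping per-arm intervals and a difference interval of 1.9 to 22.7 that excludes zero. With 10 events on 150 mg, the 300 mg arm needs 27 events (27.8%) before the planned intervals separate, but 20 events (20.6%) before the difference interval excludes zero.

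**Operating characteristics.** Full enumeration of two independent binomials with n = 97 each:

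| Assumed rates, 300 vs 150 mg | Planned intervals separate | Difference interval excludes zero |
|---|---|---|
| 5% vs 2% | 0.4% | 15% |
| 10% vs 5% | 3% | 23% |
| 12% vs 3% | 22% | 66% |
| 20% vs 5% | 59% | 91% |
| 20% vs 10% | 14% | 50% |
| 25% vs 10% | 41% | 80% |
| 30% vs 10% | 72% | 95% |
| 15% vs 15% | 0.3% | 5.0% |

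The last row shows why: with equal rates, separation of the two intervals behaves like a test at about 0.3%, not 5%.

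**Share due to the continuity correction.** At 20% versus 10%, separation is 14% with the correction and 21% without it, against 50% for the difference interval. So about 7 of the 36 lost points come from the correction and about 29 from comparing two intervals. For rarer events the correction matters more: at 10% versus 2% the figures are 18%, 34% and 65%, or about 16 of 47 points. In both cases the larger part is the two-interval comparison. The worked example overlaps even without the correction (15.5 to 32.0 against 5.7 to 17.9).

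**The case against.** The strongest reply is that the SAP nowhere says doses will be compared by overlap. Counts and percentages appear per arm, so anyone can subtract them and compute an interval. This stands. A reader might infer that the plan judges dose safety by overlap, or that it is biased towards finding no dose difference. The documents support neither: the plan omits a contrast but adopts no faulty rule.

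Second, the safety objective concerns secukinumab as a whole, whereas the comparative efficacy objectives each ask for a difference between doses. Protocol 3.2 is a rationale and promises no estimator. This also stands. It makes the addition an improvement, not the repair of a broken commitment.

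Third, a reader might infer that clear dose effects will generally be masked. That goes too far. At 30% versus 10% the planned intervals separate in 72% of trials, and at 20% versus 5% in 59%. For uncommon events, numbers are the main limit whichever display is used: at 5% versus 2% even the difference interval excludes zero in only 15% of trials.

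Fourth, the SAP contents page has a blacked-out entry just before 5.4.5, so absence can be stated for the readable text only.

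What survives is narrower. A display of separate intervals invites a comparison for which it is poorly suited, and the better estimate uses data already tabulated.

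**Conclusion.** In the readable text the plan gives adverse events per-group intervals only, with no estimate of the 300 mg versus 150 mg contrast. For moderate increases the loss of sensitivity from reading those intervals side by side is material: 14% against 50% at 20% versus 10%, and 41% against 80% at 25% versus 10%. It shrinks for large increases (72% against 95% at 30% versus 10%). The cause is mainly the comparison of two separate intervals; the continuity correction is secondary.

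These figures rest on assumed event rates and about 97 patients per arm. They describe how a reader could use the planned display, not a decision rule in the SAP. The point is a worthwhile, low-cost improvement and does not affect the efficacy analyses.

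**What to change.** In SAP 2.8.1 and 5.4.6 add, for the randomised inadequate responders in Treatment Period 2, the 300 mg minus 150 mg difference in crude incidence with a 95% Newcombe hybrid-score interval. Report it for any treatment-emergent adverse event, serious treatment-emergent events, and treatment-emergent events leading to discontinuation. Reporting by system organ class is optional. Label the results descriptive and without multiplicity control, and keep the per-arm intervals as they are.

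The cost is about one SAP sentence and one extra table column or plot panel; no new data are needed. The downside is that about 1 in 20 unadjusted intervals may exclude zero by chance when the doses do not differ, which is a reason to keep the list short.

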## 5.5 Rule of exclusion criteria of analysis sets

**Table 5-1 Protocol deviations that cause subjects to be excluded**

Deviation ID	Description of deviation	Exclusion in analyses	Severity code
D01	Patient met one or more of the Discontinuation of Study Drug criteria but study drug was not discontinued	Include in everything	0
D02	Patient voluntarily withdrew consent. However, still continuing in the study.	Exclude from everything	9
E01	Patient enrolled with total ankylosis of the spine	Include in everything	0
E02	Patient used other investigational drugs within 5 half-lives of enrollment, or within 4 weeks before the Baseline Visit, whichever is longer	Include in everything	0
E03	Patient enrolled with history of hypersensitivity to any of the study drugs or its excipients or to drugs of similar chemical classes	Include in everything	0
E04	Patient enrolled with Chest x-ray, CT scan, or chest magnetic resonance imaging (MRI) with evidence of ongoing infectious or malignant process, obtained within 3 months prior to screening and evaluated by a qualified physician	Include in everything	0
E05	Patient enrolled with previous exposure to secukinumab or any other biologic drug directly targeting IL-17, IL-12/23, or the IL-17 receptor, or any other biologic immunomodulating agent, except those targeting TNF $\alpha$	Include in everything	0
E06	Patient who took more than one anti-TNF $\alpha$ agent	Include in everything	0
E07	Patient took any intramuscular or intravenous corticosteroid injection within 2 weeks before baseline	Include in everything	0
E08	Patient took any therapy by intra-articular injections (e.g. corticosteroid) within 4 weeks before baseline	Include in everything	0
E09	Patient enrolled whose previous treatment with any cell-depleting therapies including but not limited to anti-CD20, investigational agents (e.g., CAMPATH, anti-CD4, anti-CD5, anti-CD3, anti-CD19)	Include in everything	0
E10	Patient using high potency opioid analgesics (e.g., methadone, hydromorphone, morphine)	Include in everything	0
E11	Patient enrolled with active systemic infections during the last two weeks	Include in everything	0

Deviation ID	Description of deviation	Exclusion in analyses	Severity code
	(exception: common cold) prior to baseline		
E12	Patient enrolled with active ongoing inflammatory diseases other than AS that might confound the evaluation of the benefit of secukinumab therapy, including inflammatory bowel disease or uveitis	Include in everything	0
E13	Patient enrolled with underlying metabolic, hematologic, renal, hepatic, pulmonary, neurologic, endocrine, cardiac, infectious or gastrointestinal conditions which in the opinion of the investigator immunocompromises the patient and/or places the patient at unacceptable risk for participation in an immunomodulatory therapy	Include in everything	0
E14	Patient has significant medical problems or diseases, including but not limited to the following: uncontrolled hypertension, congestive heart failure (New York Heart Association status of class III or IV), uncontrolled diabetes, or very poor functional status unable to perform self-care	Include in everything	0
E15	Patient enrolled with history of clinically significant liver disease or liver injury as indicated by abnormal liver function tests such as SGOT (AST), SGPT (ALT), alkaline phosphatase, or serum bilirubin. The Investigator should be guided by the following criteria: Any single parameter may not exceed 2 x upper limit of normal (ULN). A single parameter elevated up to and including 2 x ULN should be rechecked once more as soon as possible, and in all cases, at least prior to enrollment/baseline, to rule out lab error	Include in everything	0
E16	Patient enrolled with serum creatinine level exceeding 2.0 mg/dL (176.8 umol/L ) at screening	Include in everything	0
E17	Patient enrolled with Screening total WBC count < 3,000/uL, or platelets < 100,000/uL or neutrophils <1,500/uL or hemoglobin < 8.5 g/dL (85 g/L)	Include in everything	0
E18	Patient enrolled with Known infection with human immunodeficiency virus (HIV), hepatitis B or hepatitis C at screening	Include in everything	0

Deviation ID	Description of deviation	Exclusion in analyses	Severity code
E19	Patient enrolled with history of lymphoproliferative disease or any known malignancy or history of malignancy of any organ system within the past 5 years (except for basal cell carcinoma or actinic keratoses that have been treated with no evidence of recurrence in the past 3 months, carcinoma in situ of the cervix or non-invasive malignant colon polyps that have been removed)	Include in everything	0
E20	Patient enrolled with other clinically significant conditions (not associated with the study indication) which in the judgement of the investigator might interfere with the assessment of this study, or puts the patient at increased risk	Include in everything	0
E21	Patient enrolled with inability or unwillingness to undergo repeated venipuncture (e.g., because of poor tolerability or lack of access to veins)	Include in everything	0
E22	Patient enrolled with inability or unwillingness to receive injections with the PFS	Include in everything	0
E23	Patient enrolled with any medical or psychiatric condition which, in the Investigators opinion, would preclude the participant from adhering to the protocol or completing the study per protocol	Include in everything	0
E24	patient enrolled, and had donated or loss of 400 mL or more of blood within 8 weeks before baseline	Include in everything	0
E25	patients enrolled and had a history or evidence of ongoing alcohol or drug abuse, within the last 6 months before baseline	Include in everything	0
E26	Patient enrolled and knew he/she will be unable to complete 1 year of study treatment period	Include in everything	0
E27	Patient enrolled and has received Administration of live vaccines during the study period or 6 weeks prior to baseline	Include in everything	0
E28	Patient enrolled and has History of ongoing, chronic or recurrent infectious disease or evidence of tuberculosis infection as defined by either a positive purified protein derivative (PPD) skin test (the size of induration will be measured after 48-72 hours, and a positive result is defined as an induration of $\geq 5$ mm	Include in everything	0

Deviation ID	Description of deviation	Exclusion in analyses	Severity code
E28A	Patient enrolled with a positive central laboratory TB blood screening test and did not have further work up (according to local practice/guidelines) establishing conclusively that the patient has no evidence of active tuberculosis.	Include in everything	0
E28B	Patient had latent tuberculosis established, and then treatment was not initiated according to local country guidelines.	Include in everything	0
E29	Patient is enrolled and Pregnant or nursing (lactating) women where pregnancy is defined as the state of a female after conception and until the termination of gestation, confirmed by a positive human chorionic gonadotropin (hCG) laboratory test	Include in everything	0
E30	Patient was enrolled and Women of child-bearing potential, defined as all women physiologically capable of becoming pregnant, and did not use highly effective methods of contraception during dosing and for 16 weeks after stopping of study medication.	Include in everything	0
I01	Patient was not able to understand and communicate with the investigator and comply with the requirements of the study and must give a written, signed and dated informed consent before any study assessment is performed	Include in everything	0
I02	Patient was not male or non-pregnant, non-lactating female patients at least 18 years of age	Include in everything	0
I03	Patient did not have a diagnosis of moderate to severe AS with prior documented radiologic evidence (x-ray or radiologist's report) fulfilling the Modified New York criteria for AS	Include in everything	0
I04	Patient did not have active AS assessed by total BASDAI of $\geq 4$ (NRS of 0-10) at baseline	Include in everything	0
I05	Patient did not have spinal pain as measured by BASDAI question #2 of $\geq 4$ (NRS of 0-10) at baseline	Include in everything	0
I06	Patient did not have total back pain of $\geq 4$ on a NRS of 0-10 at baseline	Include in everything	0
I07	Patient was not taking NSAIDs at the maximum tolerated dose for at least 4 weeks prior to their Baseline Visit, with an inadequate response or for less than	Include in everything	0

Deviation ID	Description of deviation	Exclusion in analyses	Severity code
	4 weeks if withdrawn for intolerance, toxicity or contraindications		
I08	Patient was regularly taking NSAIDs (including COX-1 or COX-2 inhibitors) as part of their AS therapy was not on a stable dose for at least 2 weeks before their Baseline Visit	Include in everything	0
I09	Patient was on a TNF $\alpha$ inhibitor (not more than one) but did not experience an inadequate response to previous or current treatment given at an approved dose for at least 3 months prior to baseline or did not experience intolerance upon administration of an anti-TNF $\alpha$ agent	Include in everything	0
I10	Patient has been previously on a TNF $\alpha$ inhibitor and did not have appropriate wash-out period prior to a week before their Baseline Visit	Include in everything	0
I11	Patients taking MTX ( $\leq$ 25 mg/week), sulfasalazine ( $\leq$ 3 g/day), or leflunomide ( $\leq$ 20 mg/day) are allowed to continue their medication and must have taken it for at least 2 months and have to be on a stable dose for at least 4 weeks prior to baseline.	Include in everything	0
I12	Patients on MTX must be on a stable folic acid supplementation before their Baseline Visit.	Include in everything	0
I13	Patient was on a DMARD other than MTX, sulfasalazine or leflunomide and did not discontinue the DMARD 4 weeks prior to baseline	Include in everything	0
I14	Patient took systemic corticosteroids and was not on a stable dose of $\leq$ 10 mg/day prednisone or equivalent for at least 2 weeks before baseline	Include in everything	0
M01	Patient had concomitant intake of a prohibited medication as outlined in protocol after randomization and remained on study treatment	Include in everything	0
M02	Patient has used live virus vaccines during the study after the baseline visit. However still patient is part of study.	Include in everything	0
M03	Failure to initiate / modify concomitant medication doses according to protocol	Include in everything	0
O01	Site is not compliant to ICH GCP at any time in the study	Include in everything	0
O02	Deficient informed consent or any other process documentation at any time in the study.	Include in everything	0

Deviation ID	Description of deviation	Exclusion in analyses	Severity code
O03	Failure to perform key study efficacy procedures for example, ASDAS, BASDAI, ASAS20, ASAS40, ASAS partial remission, ADAS-Health Index, or FACIT	Include in everything	0
O04	Failure to perform safety procedure such as vitals, central labs, ECG, and pregnancy.	Include in everything	0
O06	Any other protocol deviation or observation not specified in the protocol deviations list.	Include in everything	0
O07	Missed visit due to COVID-19	Include in everything	0
O08	Visit done outside of study site due to COVID-19	Include in everything	0
O09	Assessment / procedure changed due to COVID-19	Include in everything	0
O10	Visit conducted out of window for week 12, week 16, or week 52 due to COVID-19	Include in everything	0
D03	Study/Treatment Discontinuation due to COVID-19	Include in everything	0
S01	Failure to return or failure to follow sponsor/institution for returning unused study medication	Include in everything	0
S02	Improper storage and/or accountability of study medication	Include in everything	0
S03	Incorrect study medication stock used/dispensed	Include in everything	0
S04	Improper procedure followed for Emergency Breaking of Assigned Treatment Code	Include in everything	0
S05	Any incorrect route of administration of study drug at any time during the study, per protocol	Include in everything	0
S06	Missed study drug administration at any time in the study.	Include in everything	0
S07	Patient received more injections than prescribed by protocol.	Include in everything	0
S08	Incorrect ASDAS domain [REDACTED] result entered into IRT at Baseline, Week 12 or Week 16	Include in everything	0
S09	Drug supply method changed due to COVID-19	Include in everything	0

